Methodology: Clinicians, clinic staff, and facility staff will be interviewed and multidisciplinary focus groups conducted at 3 sites to characterize the range of themes related to staff perspectives on patient reported versus clinician documented pain. Development of the enhanced pain screening protocol will account for clinician perspectives informed by qualitative input, as well as subsequent patient usability testing, and then the protocol integrated into a tablet interface will be subjected to an RCT that will be placed in primary care for selected Veterans to compare with staff administered pain screening. Veterans will be randomly allocated in a 1:1:1 ratio to the three arms and analyses will evaluate a variety of quantitative and qualitative outcomes. Veteran responses to the brief tablet based pain screening protocol and additional tablet based items will be linked to Veterans’ health data to evaluate feasibility and the association with social and clinical vulnerability (e.g., perhaps minority or cognitively impaired Veterans are particularly disadvantaged by the computer vs. in person pain assessments?). Linking to existing health data allows us to minimize the length and intrusiveness of the tablet based survey, while still assessing how social and clinical vulnerability is associated with screening measure and mode. Experience during the trial will inform implementation and be gathered through interviews with both patients and providers and clinic staff.

Results: This is a new project and results have not yet been obtained.

Significance: We will characterize how to best conduct pain screening including a direct comparison of patient reported to clinician documented pain, and selection of an optimal measure to improve clinician and patient centeredness of pain measurement (e.g., by considering the incorporation of function). This project will inform national VA implementation of a preferred measure and method.

Protocol Title: Effective Screening for Pain Protocol.....	3
1.0 Study Personnel.....	4
2.0 Introduction.....	7
3.0 Objectives.....	9
4.0 Resources and Personnel.....	10
5.0 Study Procedures.....	11
5.1 Study Design.....	11
Phase 1 Overview	11
Phase 1 procedures.....	11
a. Assess the usability of patient-self-administered pain assessment via tablet.....	13
Phase 2 Overview	14
A. Multisite RCT to test pain screening approaches via tablet:.....	14
1. Recruitment and Consenting.....	14
a. Participant Eligibility.....	14

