3.0 Objectives

The overall objective of our mixed method study is to evaluate a strategy to improve the quality and clinical usefulness of 'the 5th Vital Sign' in VA primary care. We will first develop a patient-self administered computer-aided pain assessment, then evaluate and refine the assessment using human-computer interaction laboratory usability testing. Next we will conduct a three site randomized controlled trial (RCT) to test a computer-based pain assessment protocol compared with usual pain screening. In the RCT we will evaluate three arms – one arm will use the PEG, a more sensitive screener including pain functional impairment, and a second arm will replicate the 'NRS now' allowing a direct comparison of patient-administered assessment vs. clinician assessed pain and a third arm will test the NRS at one week. All subjects will be screened with the '5th Vital Sign'. (allowing a three arm comparison of each of two computer based approaches vs. usual practice) Our specific aims are to:

Aim 1. Characterize primary care team perspectives on enhanced pain screening approaches compared with usual pain screening, including clinical usefulness and how to use skills, roles, and tasks of multidisciplinary primary care clinicians and consultants to optimize pain care. Additionally, we will try to understand Veterans' experiences with pain screening, assessment, and management (including use of opioid analgesics) in order to better link their actual experience with provider assessment and management practices. Interviews and focus groups will inform refinement of the items and screening interface; we will evaluate the interface including the PEG and 'NRS now' and the control arm for usability including among disabled veterans and for use in primary care.

Aim 2. Evaluate in a three-arm RCT the effects of enhanced pain screening approaches using a tablet and comparing the PEG, the 'NRS pain now', and usual clinician-assessed pain screening.

Hypothesis 2a: One of three enhanced pain screening approaches using the PEG, but not the 'NRS now' will be associated with improved detection of pain related disability **Hypothesis 2b:** Enhanced pain screening approaches vs. usual pain assessment will be associated with equally low missingness, Veterans, providers, and clinic and facility staff will characterize their experience with the enhanced screening protocol and important barriers, facilitators, and practical steps to inform implementation

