The 1 page field log will contain both identifiable (i.e., Full Name, last 4 digits of SSN, and contact information as needed for participation in follow up interviews) and unidentifiable data (i.e., participation status, participant ID, and observable demographics when necessary, and other research pertinent information). While in the clinic field logs will be kept on person by research staff and in a locking carrying case or secured mail bag to be transferred to a designated office. The paper documents will be stored in a locked filing cabinet inside of a locked office on VA campuses at the designated VA sites (i.e., Palo Alto, Minneapolis, Portland). A designated research assistant from each site will input the data into an encrypted and password protected Excel sheet that is kept on a secured server at VA Palo Alto. The designated research assistants at VA Portland VA Minneapolis will only have access to the cross-walk Excel sheet for their specific site. Research assistants from Palo Alto (i.e., [name] and [name]) will have access to a site specific Palo Alto Excel sheet and a master cross-walk Excel sheet that is populated by site specific crosswalks. Drs. [name] and [name] will have view only access to the master cross-walk excel sheet. At a later stage in the study, a designated programmer will have view only access to the master cross-walk excel sheet in order to compile data from both tablet survey data and medical records.

5. Tablet based survey content:

We will focus on content that is not available in existing VA administrative database the survey will include (not in this order):

- 1) an **introductory screen** which allow for registration using the unique participant number, and
- 2) **an algorithm corresponding to the three intervention arms of the RCT** and an underlying randomization engine to allocate Veterans to the three arms using a random number generator, with the corresponding pain screening measures (PEG, NRS one week, and DVPRS), and
- 3) The **Graded Chronic Pain Scale** (the gold standard for comparison),and
- 4) **Self-assessed level of physical activity**, and
- 5) **expectations and unmet need for pain treatment and management**, and

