- 6) **familiarity and experience with technology and satisfaction with the rating experience** including whether the veteran has previously used a tablet and environmental context because these items reflect previous concepts salient to pain rating variation, and
- 7) **access to and experience with smart mobile technology**

Depending on the consideration of survey length which we will prioritize to keep the survey at approximately 10 minutes, we will consider including several other items that previous research have shown to be important in considering pain outcomes including duration of pain in the previous year and the physical location of pain. In order to minimize survey burden and in order to complete our planned analyses, we will consider using VA data (rather than participant responses to obtain information about BMI, comorbidity, copay exemption status). We will also ensure physical attributes of the tablet screen best accommodate visually impaired and other physically disabled veterans where possible.

At the conclusion of the study in order to assess the degree to which implementation succeeded and Veterans who were missed by the tablet based protocol, we will compare all Veteran patients of the clinic during the study interval, as well as all Veterans who were approached but declined, with all Veteran users of the tablet during the same time by age, race / ethnicity, gender, cognitive impairment and mental health diagnoses, and NRS pain ratings, to assure that the tablet based screening process does not disadvantage any Veterans. We will gather these factors using VA electronic databases and will request a HIPAA authorization and waiver of documentation of informed consent for this portion of the study.

The usual care arm nursing staff rating of the 'NRS pain now' will be collected by linking the encounter to the Vital Signs Package to obtain the pain rating. Veterans' health records accessed in Corporate Data Warehouse and CAPRI/ VistAWeb/CPRS, will inform basic demographics and clinical factors in order to allow us to minimize the burden of the tablet protocol.

B. Patient Follow up Interviews:

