If possible, research staff will attend a local clinic staff meeting to briefly inform the staff of the study. By partnering with local clinic leadership, we plan to send emailed invitations to eligible staff members. A log of all contact attempts will be maintained and after a maximum of 3 contact attempts the staff member will be removed from the contact list.

2. Consent Process:

Prior to the interview, a research staff member will verbally consent the participant. We have approval for a waiver of documentation of informed consent. Date of consent and person obtaining consent will be logged on the secured Excel sheets stored on VA Palo Alto Servers.

3. Data Collection Procedures:

We will conduct up to 40 telephone interviews that will take approximately 20-30 minutes. The interviews will be audio recorded and later transcribed by a VA contracted transcription service. For interview questions/content please see the Provider Interview Protocol.

4. Data Security:

Any information linking identifiable information with an assigned participant ID will be located on the secured Excel sheets. These Excel sheets will be secured and stored as previously mentioned under Phase 2: a: Data Security.

Audio files will be uploaded to the secured server located at VA Palo Alto. The audio Files will be saved using the assigned participant id. Audio files and de-identified transcripts will be transferred between VA servers and the transcriptions service via an approved secured FTP server.

Figure 1: Estimated enrollment scheme for ESP

Due to randomization the proposed enrollment algorithm will allow analytic comparison of each assessment measure / mode to the other. The table below specifies the Arm to Arm comparisons but the outcomes of each comparison are ‘clinically significant pain’ defined as pain that is moderate to severe, pain that is associated with disability, or unmet need for additional management.

Main comparison (s) of interest		Arm (s)	Comment
1	Tablet: PEG vs. NRS 1 week vs. DVPRS	1 to 2 to 3 tablet comparison	Baseline arm to arm difference

Table 1: Main analytic comparisons by screening measure and mode for outcomes of detection of pain, detection of moderate / severe pain (clinically relevant), pain associated with disability and unmet needs for treatment

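### The protocol credits randomization with comparing screening modes, but all three randomised arms are tablet measures; tablet versus nurse is a paired, fixed-order contrast and is missing from Table 1

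*Protocol*

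**What the plan says.** **What is allocated.** The Abstract (Methodology) says "Veterans will be randomly allocated in a 1:1:1 ratio to the three arms". Section 5.1, Phase 2 A, item 5 (tablet survey content) puts the randomization engine inside the tablet application, "with the corresponding pain screening measures (PEG, NRS one week, and DVPRS". The Abstract's Aim 2 likewise makes DVPRS the third arm, with usual clinician screening following it.

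**How the nurse rating arises.** Section 3.0 says all subjects get the routine vital-sign pain screen. Section 5.1, Phase 2 A places the tablet before any contact with the nurse who takes vital signs. Item 5 obtains the nurse score by linking the encounter to the record.

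**What is claimed.** Before Table 1: "Due to randomization the proposed enrollment algorithm will allow analytic comparison of each assessment measure / mode to the other". Item 5 opens a sentence with "The usual care arm nursing staff rating of the" pain-now score. Section 3.0 describes the design as "allowing a three arm comparison of each of two computer based approaches vs. usual practice", and its Aim 2 lists the PEG, NRS now "and usual clinician-assessed pain screening" as the approaches compared.

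**What is analysed.** The caption of Table 1 reads "Main analytic comparisons by screening measure and mode". Its only row is "1 to 2 to 3 tablet comparison". In section 5.3, pain-related disability is analysed pairwise across arms 1, 2 and 3. The missingness row names the nurse NRS, tablet NRS and tablet PEG, and is also labelled by arms 1, 2 and 3.

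**The concern.** The trial is meant to inform whether patient-entered screening should replace or supplement nurse screening across the VA. Section 3.0 sets out to test computer-based assessment against usual screening, and the Significance paragraph of the Abstract promises a direct comparison of patient-reported with clinician-documented pain. Two things go wrong.

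- The text gives the mode comparison a randomised status that the design does not provide. A reader could take a tablet-versus-nurse difference as protected by randomization, when mode cannot be separated from order. The nurse always asks after the patient has met pain questions on the tablet.
- The list of main comparisons leaves that contrast out for every outcome in Table 1's caption. Followed as written, Table 1 ranks tablet measures against each other and does not show whether any of them detects more than usual screening.

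**Working it through.** No arithmetic applies. The protocol gives no effect size or error rate on this point, and the question is one of design structure. The check sets the sections side by side.

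**1. Is any randomised arm usual care?**

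| Place | Arms or approaches listed |
|---|---|
| Abstract, Aim 2 | PEG, NRS now, DVPRS (usual screening follows) |
| 3.0, opening paragraph | PEG, NRS now, NRS one week |
| 3.0, Aim 2 | PEG, NRS now, usual clinician screening |
| 5.1, item 5 | PEG, NRS one week, DVPRS |
| Table 1 | PEG, NRS one week, DVPRS |

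The lists disagree about which measures are used. Only Aim 2 in 3.0 puts usual screening in the place of an arm, and the opening paragraph of the same section contradicts it by naming three arms and adding that everyone also has the routine screen. The allocation step itself, in item 5, assigns tablet measures only. Count: 3 of 3 randomised arms use the tablet; 0 are usual care.

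**2. What does randomization support?**

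- Tablet measure against tablet measure, between arms: randomised.
- Difference between arms in the tablet-minus-nurse gap: randomised, but this again shows the effect of the measure assigned.
- The tablet-minus-nurse gap itself: each patient supplies both ratings, always tablet first. It is paired and not randomised, and order is inseparable from mode.

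The sentence before Table 1 is therefore right for measure and wrong for mode.

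**3. Which planned analyses include the nurse rating?**

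| Place | Outcome | Nurse rating included? |
|---|---|---|
| Table 1, one row | Detection, moderate/severe pain, disability, unmet need | No |
| 5.3 model table, row 1 | Pain-related disability | No (arms pairwise) |
| 5.3 model table, row 2 | Missingness | Yes, but labelled by arm |

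Count: 0 of 1 rows in Table 1, and 1 of 2 rows in the 5.3 model table. The missingness row matches Hypothesis 2b, which sets enhanced screening against usual assessment. Its three named measures (nurse NRS, tablet NRS, tablet PEG) stand beside the label for arms 1, 2 and 3, although the nurse rating belongs to no arm and exists in all of them.

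**4. Would a tablet-versus-nurse contrast isolate mode?** The nurse records NRS pain now. If one arm is tablet NRS now (Abstract; 3.0), that arm holds measure and recall period constant, and mode differs along with order. If the arm is NRS one week (5.1 item 5; Table 1), every tablet arm differs from the nurse rating in measure or recall period as well as in mode. No arm then isolates mode.

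**5. Against what is detection judged?** Section 5.1, item 5 names the Graded Chronic Pain Scale as the reference. The 5.3 model uses NHIS pain-related disability. A detection comparison needs one of these named as its reference.

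**The case against.** **Is the nurse comparison left wholly unanalysed?** A reader might infer so from Table 1. The documents do not support that: section 5.3 includes the nurse NRS in the missingness analysis with a logistic model, in line with Hypothesis 2b. The gap is confined to the Table 1 outcomes.

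**Will paired ratings be analysed as independent groups?** The arm wording invites that inference, but nothing in the protocol says so. It describes the within-person structure several times: all subjects have the routine screen, the tablet comes first, and the score is linked to the same encounter. If the pairing were ignored, positive within-patient correlation would make the standard error too large, which errs on the cautious side.

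**Is the missing row within Table 1's scope?** The lead-in says the table gives arm-to-arm comparisons, and a within-patient contrast is not one. That has force. But the caption promises comparison by mode, no other table supplies it for these outcomes, and the preceding sentence claims the design allows it.

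**Could Figure 1 or the SAP settle it?** Figure 1 is not reproduced in the text at hand, and the form of a paired model may properly sit in an SAP that is not shown. Neither would remove the conflict between sections 3.0 and 5.1 and the allocation they describe.

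**Is *usual care arm* just a loose label?** Probably, since the same sentence says the score comes from linkage. It recurs as a design claim in 3.0, however, so it should be corrected.

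**Conclusion.** The point holds in this form. Randomization supports comparisons among tablet measures only. The protocol wrongly extends it to mode and describes usual screening as if it were an arm. The comparison with usual screening that the Abstract and section 3.0 promise is absent for detection, moderate-to-severe pain, disability and unmet need; it appears only for missingness, under an arm label that does not fit.

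The size is structural: no randomised usual-care arm, no tablet-versus-nurse row in Table 1, and no use of the nurse rating for these outcomes, although the plan is to enrol about 650 participants, each due to have both ratings. No loss of precision or bias can be quantified from the document. The randomised comparison among tablet measures is unaffected. The conclusion rests on reading 5.1 item 5 as the operative description of allocation, which the Abstract's Aim 2 supports in that all its arms are tablet arms. The text should be corrected, because it is wrong as written on the trial's stated question.

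**What to change.** - **5.1, sentence before Table 1:** limit the appeal to randomization to comparisons between tablet measures.
- **5.1, item 5:** replace *usual care arm* with *nurse rating, collected in all arms*.
- **Abstract and 3.0:** make Aim 2 and the description of the design agree with three tablet arms plus a within-patient comparison with usual screening.
- **Table 1:** add a row for tablet measure versus nurse NRS on detection, within patient and by arm, analysed as paired data and labelled non-randomised with fixed order.
- **5.3, missingness row:** treat the nurse rating as a within-patient measurement present in every arm.
- **Arm content:** reconcile NRS now (Abstract, 3.0) with NRS one week (5.1 item 5, Table 1). Unless a tablet NRS now arm exists, describe the tablet-versus-nurse contrast as measure plus mode.
- **Reference standard:** reconcile the Graded Chronic Pain Scale (5.1 item 5) with NHIS pain-related disability (5.3).

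The cost is wording and one paired analysis on ratings already due to be linked. There is no new data collection and no change to allocation. The price in interpretation is that the conclusion about tablet versus usual screening must be stated as non-randomised.

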2.0 Introduction

Despite the importance of pain and widespread interest in patient-centeredness, the VA remains exceptional in emphasizing and successfully making pain and its management a routine feature of the health record and a focus of care. Awareness of pain and efforts to improve pain management rest on the VA's '5th Vital Sign' – a policy and practice of nursing staff routinely screening for 'pain now' at every health encounter using a 0-10 Numeric Rating Scale (NRS) (1).

Our team's previous research on the VA's '5th Vital Sign' informs the specific design of the ESP study as well as the proposed research products. (5-7) Our evaluation of routine pain screening practice in the VA identified some important concerns that keep the VA's '5th Vital Sign' from living up to its full promise:

- The "fifth vital sign" measure of current pain intensity, demonstrates limited accuracy leading to only moderate correspondence (e.g., ROC of 0.76-0.8 in two studies) for chronic disabling pain measured with the Brief Pain Inventory (BPI) (5,10), and
- Nursing staff who deliver pain assessment in about 50% of cases use informal, unstructured pain queries (e.g., 'Is your knee good today?') rather than adhering to formal use of the 0-10 NRS leading to pain underestimation, despite efforts to standardize assessment (5), and
- Linkage is missing between the current pain screening approach and improved care—pain screening information is passively available but seldom used by busy providers who act on moderate to severe pain with augmented management in only about 15% of cases. (6,7)

Several alternatives to the current pain screening approach (e.g., nurse administered 'NRS pain now' improve the sensitivity and specificity of screening for chronic pain – the optimal measure being a three item scale incorporating intensity and emotional and physical interference (e.g., the PEG). (6,7) The PEG includes items that assess physical and emotional interference, and it is very similar to the gold standard BPI from which it is derived in sensitivity, specificity, and sensitivity to change in detecting clinically important, functionally impairing pain. (6)

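### Table 1 compares detection of pain and of moderate/severe pain between arms that use different screeners, without scoring any of them against the common reference the survey collects

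*Protocol*

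**What the plan says.** The text above Table 1 (protocol, section 5.1) relies on randomisation to allow each measure to be compared with the others. It names clinically significant pain as the outcome, "defined as pain that is moderate to severe, pain that is associated with disability, or unmet need for additional management". No instrument or cut-point is given for moderate to severe.

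Table 1 has one row, "Tablet: PEG vs. NRS 1 week vs. DVPRS", with the comment "Baseline arm to arm difference". Its caption gives the comparisons "for outcomes of detection of pain, detection of moderate / severe pain (clinically relevant", followed by pain with disability and unmet need for treatment.

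The tablet content list (section 5.1, Phase 2, part A, item 5) describes random allocation to three arms "with the corresponding pain screening measures (PEG, NRS one week, and DVPRS". The next entry, not tied to any arm, is the Graded Chronic Pain Scale, described as "the gold standard for comparison".

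Section 2.0 describes the PEG as "a three item scale incorporating intensity and emotional and physical interference (e.g., the PEG". It describes the existing fifth-vital-sign NRS as a measure of current pain intensity.

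Section 5.3 lists two quantitative models: a linear regression for NHIS pain-related disability and a logistic regression for missing ratings. Neither uses the Graded Chronic Pain Scale, and none of the listed analyses concerns sensitivity, specificity or ROC area.

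**The concern.** Each Veteran answers one of the three screeners. Unless detection is tied to a measure that every arm completes, detection of pain and of moderate/severe pain has to be read from a different scale in each arm. The scales differ in content: the PEG adds interference to intensity, and the NRS rates intensity only. The same person can therefore be positive in one arm and negative in another.

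A positive rate also does not separate true from false positives. Lowering a cut-point raises it whether or not the extra positives have clinically significant pain.

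The abstract says the project should select an optimal measure and inform national implementation of a preferred one. That choice needs accuracy. A difference in how often each scale flags patients does not supply it.

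**Working it through.** **No figure to reproduce.** The protocol states no detection rate, cut-point, effect size or power for these outcomes. What follows is illustration on stated assumptions.

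**1. One patient, two scales.** Assume the PEG is scored as the mean of three 0-10 items; the protocol does not give its scoring. With intensity 7 and interference 1 and 1, the NRS is 7 and the PEG is (7 + 1 + 1)/3 = 3. At a cut-point of 4 this person is positive on the NRS and negative on the PEG.

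**2. Two arms with identical true pain.** Assumptions, none from the protocol: correlated normal items, rounded and truncated to 0-10; intensity mean 4 (SD 2.7); two interference items with mean 3 to 4 (SD 3.1); inter-item correlation 0.5 to 0.7; NRS equal to the intensity item; 1,000,000 simulated patients per setting. The DVPRS is not simulated.

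| Cut-points | NRS positive | PEG positive | NRS minus PEG |
|---|---|---|---|
| NRS ≥4, PEG ≥4 | 57% | 42-53% | about +4 to +15 points |
| NRS ≥5, PEG ≥5 (interference mean 3.5, correlation 0.6) | 43% | 32% | about +11 points |
| NRS ≥5, PEG ≥4 | 43% | 42-53% | about 0 to −10 points |

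In the first row, 16% to 24% of individuals are classified differently by the two scales. The arms have the same pain throughout, yet the sign of the difference changes with the cut-points.

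**3. Flag rate against accuracy.** Section 2.0 reports ROC areas of 0.76-0.8 for the current NRS. Use an equal-variance binormal model with d′ = √2 × z(AUC), sensitivity = 1 − Φ(z(specificity) − d′), and flag rate = prevalence × sensitivity + (1 − prevalence) × (1 − specificity). Assume 30% prevalence.

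- Same accuracy, different cut-point. AUC 0.78 gives d′ = 1.092.
  - Specificity 0.80: sensitivity 0.599; flag rate 0.3 × 0.599 + 0.7 × 0.20 = 0.320.
  - Specificity 0.60: sensitivity 0.799; flag rate 0.3 × 0.799 + 0.7 × 0.40 = 0.520.
- With 650/3 ≈ 217 per arm (section 5.1 enrolment, 1:1:1 allocation) and an assumed two-sided alpha of 0.05, the standard error of that difference is √[(0.32 × 0.68 + 0.52 × 0.48)/217] ≈ 0.046. A difference of 0.20 is then significant about 99% of the time, although the screeners are equally accurate.
- Unequal accuracy.
  - AUC 0.80 at specificity 0.80: sensitivity 0.636, Youden index 0.636 + 0.80 − 1 = 0.436, flag rate 33%.
  - AUC 0.76 at specificity 0.60: sensitivity 0.772, Youden index 0.772 + 0.60 − 1 = 0.372, flag rate 51%.
  - The less accurate screener has the higher raw rate.

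Sensitivity taken alone also ranks these two the wrong way (0.772 against 0.636). A common reference is therefore necessary but not sufficient. The comparison also needs a summary that does not move with the cut-point, such as ROC area.

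**The case against.** The strongest reply is that the protocol already points to the right reference. The Graded Chronic Pain Scale follows the three screeners in the survey list and is called the gold standard. Section 2.0 discusses screening in terms of ROC, sensitivity and specificity. Cut-points and scoring could reasonably be left to an analysis plan that is not shown. This stands in part: the intention can be inferred and the repair is simple. But Table 1 sets the outcomes and the contrast, neither it nor section 5.3 uses that scale, and cut-points alone would not make a raw rate a measure of accuracy.

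A reader might infer more than the protocol supports:

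- **That over-flagging is counted as success.** No section says that the higher percent positive wins or that it selects the measure. Section 5.3 has no model for percent moderate/severe.
- **That every arm difference is an artefact.** Comparing scales is the purpose of the trial, so a scale effect is intended. The fault is that a raw rate cannot separate true from false positives.
- **That the comparison works against Hypothesis 2a.** That hypothesis (section 3.0) concerns detection of pain-related disability, not percent moderate/severe.
- **That the NRS would be favoured.** This follows from equal cut-points in the simulation. With 5 for the NRS and 4 for the PEG the gap disappears or reverses.

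**Conclusion.** The concern holds as a mismatch between the outcomes in Table 1 and the reference standard in the survey. As written, detection of pain and of moderate/severe pain is an arm-to-arm difference on different scales, and that difference cannot show which screener is more accurate. This conclusion rests on the text and on randomisation, not on the simulation.

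The size is illustrative only. On the assumed inputs, NRS minus PEG runs from about +15 to about −10 percentage points with no difference in true pain, depending on cut-points and item distributions. PEG scoring, item means, SDs, correlations, cut-points, prevalence, specificity and alpha are all assumptions, and nothing was computed for the DVPRS.

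**What to change.** In Table 1 and section 5.3:

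1. Define detection of pain and of moderate/severe pain against the Graded Chronic Pain Scale, and state how each participant is classified on it as reference-positive or reference-negative.
2. Compare the screeners between arms by area under the ROC curve. Add sensitivity (share of reference-positive Veterans flagged) and false-positive rate (share of reference-negative Veterans flagged), at a cut-point fixed in advance for each screener.
3. Report raw percent positive by arm as description only.
4. Reconcile the gold standard named in the tablet content list with the NHIS disability measure in section 5.3, and say which measure serves the disability and unmet-need parts of clinically significant pain.

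The cost is wording, with no new data for the first three items, and some precision. At an assumed 30% prevalence, about 0.3 × 217 ≈ 65 Veterans per arm are reference-positive. For a sensitivity of 0.60 the 95% half-width is 1.96 × √(0.6 × 0.4/65) ≈ 0.12, against 1.96 × √(0.6 × 0.4/217) ≈ 0.07 for a proportion of 0.60 in the whole arm.
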